D.9.b. Missing Data. Because the main predictors of interest, intervention arm and demographics, are collected at baseline, we do not anticipate much missing data in these variables. There may be missing values in the outcome measures due to drop-out, a missed interim assessment, or item non-response. Given a thorough understanding of the missing data mechanism, it is possible to use all of the available information in analysis, rather than using only subjects with completely observed information. Our main analysis technique, general linear mixed models via maximum likelihood estimation, implicitly accommodates missingness when missingness is due either to treatment, to prior outcome, or to other baseline covariates included in the model (81), defined as missing at random (MAR). Therefore, inferences will be valid even if we have differential dropout by intervention arm. If the missing values are related to other measured patient factors, such as age, gender, or employment status, then multiple imputation (MI) provides a framework for being able to incorporate information from these auxiliary variables while still preserving a parsimonious main treatment effect model (82) and is described as a significant advantage in recommendations from Panel on Handling Missing Data in Clinical Trials (2010) (83). Depending on the type and scope of missing data MI will be conducted via the SAS procedure PROC MI or the SAS macro IVEware (http://www.isr.umich.edu/src/smp/ive/) (84). If the probability of dropout is related to the actual missing response (which is unobserved because it is missing) or to other unobserved quantities, the missing data due to dropout is considered missing not at random (MNAR) or nonignorable (85). There is a possibility that data may be MNAR, and we propose as additional sensitivity analyses to explore MNAR methods, including selection and pattern-mixture models as recommended by Molenberghs and Kenward (86).

D.9.c. Intent-to-Treat Analysis. All of the proposed primary and secondary analyses focus on the effect of GPC as compared to usual care. We, therefore, plan to use the intent-to-treat assumption for all analyses.

D.9.d. Primary Analysis. The GPC vs usual care comparison in Framingham risk score change from baseline to month 6 will be examined with the following general linear mixed model,

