 $Y_{ijt} = \beta_0 + \beta_1 int^* month6 + \beta_2 month12 + \beta_3 int^* month12 + \beta_4 site + \beta_5 gender + \beta_6 smoking + c_j int^* month6,$

where Y_{ijt} is Framingham risk score for subject *i* in group *j* at *t*=month0, month6. We will estimate the parameters in the model using the SAS procedure MIXED (Cary, NC), and we will test to see if there is a difference in mean FRS change at month 6 between the GPC and usual care arm, i.e., $\beta_1 < 0$. The way time is coded in this model is often referred to as a constrained longitudinal data model (cLDA) (87) in which the month 0 risk is modeled as a dependent variable in conjunction with the constraint of a common month0 mean across the treatment arms. In this way, the cLDA model is comparable to an ANCOVA model; the two models are equivalent when there is no missing data. However, unlike an ANCOVA, subjects who are missing the month 6 measurement are included in the model because baseline is part of the response vector. As recommended by the CPMP (80), the model will also be adjusted for stratification variables of site, gender, and smoking status for improvement in precision. We will use an unstructured covariance to account for the correlation between repeated measurements, and we include a group-level random effect for intervention arm

patients, c_i, to account for the intra-class correlation between patients in the same prevention group. Similar procedures will be used to assess change through month 12 as a secondary analysis.

D.9.e. Aim 2 Analyses. Similar to the FRS, the secondary outcomes are all continuous and measured at baseline, month 6, and month 12. Analyses of these outcomes will thus proceed as describe above for FRS.

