D.9.f. Aim 3 Analyses. The analyses for Aim 3 will only include the intervention arm patients and will be exploratory in nature. The primary outcome for these analyses will be change in FRS from baseline to month 6. We will consider multiple ways of characterizing group cohesion, including: each individual's group cohesion score at the last group session; each individual's change in group cohesion from the first to the last group session; and, the mean group cohesion score at the last group session will be examined with a linear mixed-effects model, where additional predictors will include gender, smoking status, site, race, and age. A random effect for group membership will be included in the model to account for the intra-class correlation between patients in the same prevention group. Because the main predictors in these analyses are measured throughout the intervention, these analyses may be more impacted by drop-out or missed interim assessments than the Aim 1 and 2 analyses. We plan to use multiple imputation as the primary approach for handling missing data for the Aim 3 analyses.

D.9.e. Sample Size Calculations. The primary aim is to determine if there is a significant GPC vs usual care improvement in the mean FRS change from baseline to month 6. The clinically relevant mean FRS change is 2.0%. We assumed that FRS is normally distributed, and set the type-I error rate at α = 0.05 and the

type-II error rate at β = 0.20, representing power at 80% to detect significant differences. To take the intra-class correlation (ICC) among the group members in the GPC into consideration, we

applied the sample size procedures for group-randomized designs of Donner and Klar (88). Let *m* be the number of participants in each of the prevention coaching groups, and let ρ represent the ICC among the members of the group. In general, the minimum number of participants in each treatment arm is given by, $n = (Z_{1-\alpha/2} + Z_{1-\beta})^2 (2\sigma^2) [1 + (m-1)\rho] / (\mu_{GPC} - \mu_{UC})^2.$

Here, Z_p is the *p*-th percentile from the standard normal distribution, while μ_{GPC} and μ_{UC} is the anticipated mean change for the GPC and usual care arms, respectively. However, this formula is not quite right for this study – the control condition is usual care, and no ICC is anticipated among its members. As a result, the formula is modified to,

 $n = (Z1 - \alpha/2 + Z1 - \beta)^2 \{\sigma^2 + \sigma^2 [1 + (m - 1)\rho]\} / (\mu 1 - \mu 2)^2.$

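### The plan names maximum likelihood and no degrees-of-freedom method for mixed models whose clustering rests on about 20 groups: a slight effect on the primary test, a clearer one on the exploratory group-mean cohesion test

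*Combined protocol and SAP*

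**What the plan says.** D.9.b (Missing Data) gives the main technique as "general linear mixed models via maximum likelihood estimation", in explaining why incomplete outcome data can be used under a missing-at-random assumption. D.9.d (Primary Analysis) states "We will estimate the parameters in the model using the SAS procedure MIXED" and gives no estimation option. It adds: "we include a group-level random effect for intervention arm" patients. Aim 2 and the month-12 comparison follow the same approach.

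D.9.f (Aim 3 Analyses) "will only include the intervention arm patients and will be exploratory in nature". It lists three ways to characterise cohesion: the individual's last score, the individual's change in score, and a group-level one, where "the mean group cohesion score at the last group session will be examined with a linear mixed-effects model". The model there is specified as follows: "additional predictors will include gender, smoking status, site, race, and age"; "A random effect for group membership will be included in the model". Multiple imputation is the primary approach to missing data in this aim. D.9.f does not restate the estimator, so applying the D.9.b wording to it is an inference, though a fair one.

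No section mentions REML, Kenward-Roger, Satterthwaite, between-group degrees of freedom or any other small-sample adjustment.

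**The concern.** Maximum likelihood (ML) makes no allowance for the fixed effects when it estimates variance components, so with few clusters the between-group variance is biased downward. A normal reference, or a t reference on residual degrees of freedom, then treats that variance as better known than it is. Both push towards intervals that are too narrow and tests that reject too often.

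The plan takes clustering seriously at the design stage: its sample-size formula carries a design effect in the GPC arm. The stated estimator gives back a little of that protection at analysis. The primary test is partly shielded because the usual-care arm is unclustered. The group-mean cohesion score is not shielded, because it takes only about 20 distinct values, one per group.

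**Working it through.** **Inputs.** From Sample Size Calculations (also numbered D.9.e): SD of change 6.3, ICC 0.03, group size 10, difference 2.0, two-sided 5% (the formula uses Z at 1-α/2), power 80%, 180 per arm, 10% attrition, 400 enrolled. Assumed: equal arms (implied by 180 per arm), balanced groups, covariate prevalences, ICCs of 0, 0.05 and 0.10, and an ICC of 0.2 for cohesion itself in one Aim 3 simulation.

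**1. The plan's own figures.** n = (1.960 + 0.842)² × 6.3² × {1 + [1 + 9 × 0.03]} / 2.0² = 7.849 × 39.69 × 2.27 / 4 = 176.8, so 177 per arm against 180 stated. Then 360 / 0.9 = 400. The SD also checks: √(2 × 14² × (1 - 0.9)) = 6.26.

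**2. Number of groups.** 400 / 2 = 200 GPC patients, and 200 / 10 = 20 groups, with about 9 analysed per group after attrition.

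**3. Primary test, approximate degrees of freedom.** With 180 analysed per arm, the variance is 39.69 / 180 = 0.2205 for usual care and 0.2205 × (1 + 8 × 0.03) = 0.2734 for GPC. The SE is √0.4939 = 0.703. Satterthwaite df = 0.4939² / (0.2205²/179 + 0.2734²/19) ≈ 58, so the critical value is 2.002 rather than 1.960. Usual care supplies 0.2205 / 0.4939 = 45% of the variance, which is why the effect is small.

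**4. Aim 3 group mean, approximate size.** Intercept, site and mean cohesion vary only between groups, leaving 20 - 3 = 17 df (critical value 2.110). If the between-group variation is divided by 20 instead of 17, the SE shrinks by the factor √(17/20) = 0.922, about 8%. At a low ICC the group variance is often estimated as zero, which limits how far ML can fall below the truth.

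**5. Simulation under the null, 20 groups of 9.** There were 20,000 trials per setting (40,000 for the change-score runs at ICC 0.03). The Monte Carlo standard error at 20,000 is √(0.05 × 0.95 / 20,000) = 0.15 points.

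Primary month-6 test:

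| ICC | Model | ML SE / true SE | ML, normal | ML, t(19) | REML, normal | REML, Satterthwaite |
|---|---|---|---|---|---|---|
| 0.03 | baseline-adjusted | 0.675/0.686 = 0.984 | 5.4% | - | - | 4.5% |
| 0.03 | change score | 0.987 | 5.6% | 4.2% | 5.2% | - |
| 0.10 | baseline-adjusted | 0.741/0.772 = 0.960 | 6.5% | - | - | 5.1% |
| 0.10 | change score | 0.967 | 6.2% | 4.7% | 5.6% | - |

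Further runs at ICC 0.03 gave 5.8-5.9% for ML with a normal or residual-df reference and 4.2% with t(19). At ICC 0 there was no inflation (4.8%). At ICC 0.05 the ML normal-reference rate was 5.5-6.2%.

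Aim 3 group-mean cohesion (change-score model):

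| ICC | ML SE / true SE | ML, normal | ML, t(17) | REML, normal | REML, t(17) |
|---|---|---|---|---|---|
| 0.03 | 0.951 | 7.0% | 5.2% | 5.6% | 4.0% |
| 0.10 | 0.919 | 8.6% | 6.8% | 6.6% | 4.9% |

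ML with residual df gave 6.6% and 8.5% at the same two ICCs. Further runs at ICC 0.03 gave 6.6-6.8% under ML and 5.2-5.3% under REML with the same kinds of reference.

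REML alone, with the normal reference kept, removes 1.4 of the 2.0 excess points at ICC 0.03 and 2.0 of 3.6 at 0.10, so most of the excess goes with ML. Changing only the df removes 1.8 points at each ICC, so the split depends on the order taken, and both are needed at ICC 0.10.

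**6. Power of the corrected primary test at ICC 0.03.** By the step 3 figures: 2.0/0.703 - 1.960 = 0.886, or 81.2%, with a normal reference, and 2.0/0.703 - 2.002 = 0.844, or 80.1%, with 58 df. In the baseline-adjusted simulation, ML with a normal reference gave 83.9% and REML-Satterthwaite 81.2%. The loss is about 1 to 3 points.

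**The case against.** The strongest reply is that the ML phrase sits in the missing-data section and may only mean likelihood-based. D.9.d names PROC MIXED without a method option, and REML is that procedure's default. If REML is meant, the primary test is close to nominal (4.8-5.2% at ICC 0.03 across references and runs) and the Aim 3 group-mean test is at 5.2-5.6%. This stands as a reading of the text, and it is why the point is conditional on following D.9.b literally. The wording should still match what will be run.

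Second, the plan states no normal reference. With between-group df the primary test does not exceed 5% even under ML. This stands too. It also shows that the unstated choice moves the result, so it should be fixed in advance.

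Third, the corrected test is itself mildly conservative at the planned ICC (about 4.5% primary, about 4% for the Aim 3 group mean), so it does not land exactly on 5% there. True. It is near 5% at ICC 0.10 (5.1%, and 4.8-4.9%).

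Fourth, the simulations are stand-ins. They use a single follow-up comparison rather than the constrained longitudinal model with unstructured covariance, and complete cases rather than multiple imputation in Aim 3. Direction and ordering should carry over, because imputation does not create more groups, but the exact rates may not.

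ICCs above 0.03 are assumptions. They are worth examining because the 0.03 comes from the earlier diabetes group-visit trial, whose group strategies B.6.c describes as wholly unlike the proposed one.

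**Conclusion.** The point holds as a minor one. If D.9.b is followed literally, the primary standard error is about 1-2% too small at ICC 0.03 (type I error 5.4-5.9% with a normal reference, not inflated with between-group df) and about 3-4% too small at an assumed ICC of 0.10 (6.1-6.5%). For group-mean cohesion the type I error is about 6.6-7% and 8-8.6% respectively.

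A reader might infer that the primary result is unreliable or the trial under-sized. The documents do not support that: at the only ICC they give, the primary effect is negligible and depends on a reference distribution they do not state, and the 180 per arm reproduces. A reader might also infer that the whole test of H3A is invalid. That goes too far: the clear effect falls on one of three cohesion measures, the roughly 17-df argument does not apply in the same way to the two individual-level scores, and D.9.f labels the aim exploratory.

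**What to change.** In D.9.b, D.9.d, D.9.e (Aim 2 Analyses) and D.9.f, state that the linear mixed models are fitted by REML, with Kenward-Roger or Satterthwaite degrees of freedom for fixed-effect tests and intervals (choose one). Apply this to the month-6 and month-12 contrasts, the Aim 2 outcomes and the Aim 3 cohesion terms. For Aim 3, add that the multiply imputed results are pooled with between-group complete-data degrees of freedom (about 17 for the group-mean score). ML can be kept for comparing mean structures.

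REML uses the same incomplete data under the same missing-at-random assumption, so the rest of D.9.b is unaffected. The cost is a sentence of plan wording and two procedure options, slightly wider intervals, a mildly conservative test at ICC 0.03, and about 1-3 points of power, which stays at about 80-81%. No new data and no change to the sample size are needed.

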D.3.a. Framingham Risk Score. FRS (64) is calculated using age, gender, blood pressure, total and HDL cholesterol, smoking status, diabetes status, and status of taking blood pressure medication; we are excluding diabetic patients (see D.3.a.ii below). As such, all patients in the study will have hypertension with less-than-optimal control, **OR** elevated total cholesterol, **OR** be a current smoker. The table shows some typical FRS risk profiles. The examples are all male non-smokers:

	Subject A1	Subject A2	Subject B1	Subject B2	Subject C1	Subject C2	
Age	50	50	55	55	55	55	
SBP (on med)	-	-	-	-	140	-	
SBP (no med)	135	135	160	140	-	140	
Total cholesterol	210	190	190	190	190	190	
HDL	35	45	45	45	45	45	
10 yr FRS	7%	5%	9%	7%	9%	7%	

D.3.b. Rationale for 5% risk, with 2% reversibility. We are targeting a group of primary prevention patients that are relatively sick for primary prevention. A 2% reversibility is chosen because this is approximately the effect size seen in our study of a similar intervention among non-VA users; 5% baseline risk is chosen because patients with lower risk than this likely will not justify this relatively intensive intervention (nor, often, have 2% reversibility).

D.3.c. Process for identifying eligible patients. We will use a multi-phase process to identify patients that fit this demographic, reviewing aggregated local CPRS data first, then reviewing individual charts, then interviewing patients and obtaining lab data. We will target enrolling 200 from each site (Durham and Buffalo).

D.3.c.i Accrual of potential eligible patients from database: Patients will be initially identified from local VA administrative data (or VINCI, depending on VA policy at that time). In the database phase, identification will use the following inclusion and exclusion criteria:

 Inclusion: a diagnosis of inadequately controlled hypertension, as defined by an outpatient ICD-9 code of 401.x and a most recent blood pressure with either systolic > 140 mmHg or diastolic > 90 mmHg, **OR** (2) inadequately controlled dyslipidemia, as defined by most recent total cholesterol > 200 mg/dl **or** HDL cholesterol < 35 mg/dl, **OR** (3) current smoking, which can be identified using the CPRS Health Factor tied to the smoking clinical reminder. Medication-taking status for these illnesses is neither required nor excluded.

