D.3.c.ii First contact of potentially eligible patients: Patients who are eligible by database criteria will be contacted by letter, asking them to call a toll-free number if they do not wish to be called for the study, or if they wish to consider enrollment. Those who do not call within 1.5 weeks of mailing letters will have medical records reviewed by study personnel.

D.3.c.iii Chart review phase exclusion: We will exclude patients whose electronic medical record reveals any of the diseases that are exclusions in the database phase above, or which contradicts the database inclusion (for example, a patient who has quit smoking since the last completion of the smoking cessation reminder). We will also, at this phase, exclude patients with other severe intercurrent illness or poor life expectancy, as defined by: Active treatment of any malignancy, except for hormone treatment for breast or prostate cancer; renal dialysis or cirrhosis of the liver; psychiatric hospitalization within the last 3 years, or requirement for oxygen at any waking hour.

We will also exclude patients who appear in the electronic medical record to be currently engaged in formal efforts to improve a CV risk behavior, including: enrollment in smoking cessation clinic in the last 6 months; MOVE! enrollment within the last 6 months, or intentional weight loss of at least 5 pounds in the last 3 months.

Any patient not excluded at this time will be contacted by phone for the study. Interested patients will be have their inclusion and exclusion criteria reviewed over the phone. This will include all criteria mentioned previously as well as the Short Portable Mental Health Status Questionnaire (65) to determine cognitive impairment. Finally, the RA will also ask the patient if s/he has set a quit date for smoking, or has enrolled in a community-based weight loss or physical activity program; a "yes" answer to either of those will exclude the patient. If the patient is still eligible and interested, s/he will be asked to set up a time and place for enrollment (see D.4, below).

D.3.c.iv. Interview and lab phase inclusion and exclusion. As part of the enrollment visit, blood pressure and cholesterol will be measured (see below); patients who lose their eligibility due to improvement of either of these parameters will also be excluded prior to randomization.

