Once patients have completed the measurement battery and blood draw, we will prepare to randomize them to receive or not receive the GPC intervention. To maintain blinding, patients will be randomized remotely from the enrollment, and the blinded research assistant will not provide the assignment. Instead, the research assistant will obtain a date, time, and working phone number for a randomization phone call to be made (within 3 business days) by the research assistant from the other site (Durham vs. Upstate New York). This delayed randomization is also required in order to allow lipid testing to be completed, so that patients with a baseline FRS of < 5%, or lack of reversible risk, may be excluded. *To maintain subject engagement, intervention patients will be mailed "Moving Forward," a VA-approved primer on Problem-Solving, after randomization (see D.4.a below).*

Participating individuals will be followed for 12 months. The intervention lasts only 6 months; however, patients are in theory being taught lasting skills in the intervention. It is therefore an important question to determine if the effects of the intervention (if any) extinguish after contact with the program ends. The local RA will ascertain the measurement battery at baseline, 6, and 12 months. At all follow-up visits, the RA assigned to measure outcome variables will be blinded as to which group the patient is randomized. Patients will receive \$50 compensation for each scientific visit, for a total maximum of \$150 for the scientific visits.

D.4.z. Pilot Study. The first 10 patients enrolled into the study will be part of a pilot cohort. They will not be randomized; instead, all 10 will be assigned to the intervention (section D.5 below). These patients will have the same patient experience as patients randomized to the intervention arm (D.4.a below). This is being done to determine if the intervention needs modification prior to implementation in the study. These patients will sign a separate, clearly marked consent form notifying them that they are in a pilot study; however, the risks of the pilot are essentially identical to the risks of the planned trial.

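### The printed primary equation omits the month-6 main effect, so β1 is not the between-arm difference that the text says it tests

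*Combined protocol and SAP*

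**What the plan says.** The equation in D.9.d (Primary Analysis) has the fixed part "\beta_0 + \beta_1 int^* month6 + \beta_2 month12 + \beta_3 int^* month12", followed by site, gender and smoking, and a group random effect for intervention patients at month 6. Month 12 has both a main effect (β2) and an interaction (β3). Month 6 has only the interaction (β1).

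The text of the same section describes the analysis in three ways:
- The test: "we will test to see if there is a difference in mean FRS change at month 6 between the GPC and usual care arm", expressed as β1 < 0.
- The constraint: baseline is part of the response vector, "in conjunction with the constraint of a common month0 mean across the treatment arms". No other constraint on the means is described.
- The relation to ANCOVA: "the two models are equivalent when there is no missing data".

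The Sample Size Calculations (the second section numbered D.9.e) define a separate anticipated mean change for each arm and use a two-sided Z(1-α/2). The Aim 2 section carries the method to the secondary outcomes: "Analyses of these outcomes will thus proceed as describe above for FRS".

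**The concern.** Without a stand-alone month-6 term, the model's usual-care mean at month 6 is β0 plus covariates, which is also its baseline mean. This second constraint is not described anywhere in the text. It sets usual care's mean change to zero, although the sample-size section gives that arm its own mean change. The coefficients run from β0 to β6 without a gap and the text names β1 as the test, so text lost from the PDF is an unlikely explanation.

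If the model is programmed as printed, a fall in FRS common to both arms is credited to GPC, and a common rise hides part of a real benefit. Randomization does not protect against this, because the month-6 control data no longer serve as the comparator.

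A non-zero shared change is plausible, but its size and sign are unknown:
- Some patients enter on poorly controlled blood pressure or lipids, which favours regression to the mean. Others can enter on smoking alone: "current smoking, which can be identified using the CPRS Health Factor tied to the smoking clinical reminder" (D.3.c.i).
- Selection also acts on the enrollment values: "patients who lose their eligibility due to improvement of either of these parameters will also be excluded prior to randomization" (D.3.c.iv), and "patients with a baseline FRS of < 5%, or lack of reversible risk, may be excluded" (D.4).
- Usual care continues during follow-up.
- Age is an FRS input (D.8.a) and pushes the score up.

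**Working it through.** **Inputs from the Sample Size Calculations.** SD of FRS σ = 14, 6-month correlation ρ = 0.9, SD of change 6.3, ICC 0.03, groups of 10, n = 180 per arm (18 GPC groups), difference 2.0, two-sided α = 0.05. Equal SDs at both visits is an added assumption.

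**1. The plan's own figures.** The SD of change is 14 × √(2 × 0.1) = 6.26, which agrees with 6.3. The plan's formula gives n = (1.960 + 0.842)² × 6.3² × (1 + 1 + 9 × 0.03) / 2.0² = 176.8, or 177 per arm against the stated 180. Attrition: 360 / 0.9 = 400. The plan's figures are reproduced within 3%.

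**2. What β1 estimates as printed.** Only the GPC month-6 mean is free. Generalized least squares therefore gives

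β1 = (GPC month-6 mean) − ρ × (GPC baseline mean) − (1 − ρ) × μ,

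where μ is the estimated common mean. It pools the GPC baseline mean with the average of usual care's baseline and month-6 means, which gets weight 2/(3 + ρ). If both arms change by d, that usual-care average moves by d/2, so μ moves by d/(3 + ρ). The share of d that enters β1 is

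1 − (1 − ρ)/(3 + ρ) = 1 − 0.1/3.9 = 0.974.

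With a month-6 main effect the share is 0. Adding month 12 with free means in both arms (complete data), or adding the group effect, leaves 0.974 unchanged.

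**3. Standard errors.** The group variance is 0.03 × 6.3² = 1.19, which contributes 1.19/18 = 0.066.
- ANCOVA: √(196 × 0.19 × 2/180 + 0.066) = 0.693.
- Model with month 6 added: 0.693.
- Printed model: √(196/180 × [0.19 + 0.01 × 1.9/3.9] + 0.066) = 0.528.

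The printed model is therefore not equivalent to ANCOVA, and this needs no assumption about drift.

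**4. Type I error, with no true arm difference.** Two-sided rejection is Φ(−1.96 + k) + Φ(−1.96 − k), with k = 0.974|d|/0.528 (unrounded values used). The documents give no usual-care change, so the values of d are illustrative except −0.13. That value is the regression to the mean implied by the 5% FRS floor alone: N(29, 14) truncated at 5 has mean 30.34, and 0.1 × 1.34 = 0.13.

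| Shared change d | Bias in β1 | Type I error | Simulated |
|---|---|---|---|
| 0 | 0 | 5.0% | 4.9% |
| −0.13 | −0.13 | 5.7% | 5.3% |
| −0.25 | −0.24 | 7.5% | 7.0% |
| −0.5 | −0.49 | 15% | 14% |
| −1 | −0.97 | 45.5% | 42% |
| −2 | −1.95 | 96% | 95% |

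The simulation used 1,500 runs per row, with the residual covariance estimated and the group variance fixed. In a separate simulation of 2,000 runs without the group effect, the model with month 6 added rejected in 4.6% to 6.3% of runs for shared changes from 0 to −4.

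**5. Power with a shared rise of 1 and a true effect of −2.0.** The printed model's expected estimate is −2.0 + 0.974 = −1.03, and power is Φ(1.03/0.528 − 1.96) = 49%. The correct model has power Φ(2.0/0.693 − 1.96) = 82%. Simulation gave 50% and 84%.

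**6. Sensitivity.** Absorption is 95% at ρ = 0.8, 92% at 0.7 and 86% at 0.5. At ρ = 0.9 it is 84% if the month-6 SD is 12 and 99.8% if it is 16. At ρ = 0.7 the type I error for d = −1 is 20% rather than 45.5%.

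**The case against.** The strongest reply is that the intended analysis is clear everywhere except in this one line. The text names the constrained longitudinal model, places its only constraint at month 0, and powers the trial on a between-arm difference in change. Nor can the equation be programmed alone: it shows no residual term, lists t as months 0 and 6 while carrying month-12 terms, and leaves the covariance to the text. A competent programmer would probably restore the missing term. Harm also needs a usual-care change whose size the documents do not give, and the one drift derivable from the plan's inputs (−0.13) is nearly harmless. The 97% depends on ρ = 0.9 and equal SDs. The by-arm summaries and mean trajectory plots planned in D.9.a would probably reveal a common shift.

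Much of this stands. The slip is probably clerical, the larger error rates are conditional, and no magnitude carries over to the Aim 2 outcomes, for which the plan gives no SD or correlation. It does not remove the defect. The equation names β1 as the test coefficient, so literal coding is possible, and equation and text now define two primary tests with different standard errors. Descriptive plots do not replace a correctly specified test.

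**Conclusion.** The concern holds, and the equation must be corrected before analysis. It contradicts the text of its own section and the sample-size section, and it is the only primary equation in the plan. That conclusion rests on the documents alone.

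The size is conditional. Under the plan's covariance with equal SDs, β1 takes up 97% of a shared change. Over the correlations from 0.5 to 0.9 and month-6 SDs from 12 to 16 that were checked one at a time, the share runs from 84% to 99.8%. Actual bias arises only if the model is coded as printed and usual care changes by month 6. With no usual-care change the type I error is 5%; with a shared change the error can run in either direction.

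**What to change.** Print the mean model as β0 + β1 month6 + β2 int*month6 + β3 month12 + β4 int*month12 + β5 site + β6 gender + β7 smoking, with t = month 0, 6, 12 to match the month-12 terms already in the equation. Name β2 (int*month6) as the primary test, two-sided at 5%, to match the Z(1-α/2) used for sample size. State that the group random effect for intervention patients also applies to the month-12 contrast.

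With dropout, including month 12 can alter the month-6 estimate, so the choice of t should be explicit. Aim 2 inherits the corrected form.

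The cost is one added term, renumbered coefficients and matching PROC MIXED code. Sample size, visits and data collection do not change, because the sample-size formula already compares changes between arms.
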